8.4 Allocation of the study drug and administration procedure

The principal investigator or the designee shall access the Case Registration Web System to allocate the study subjects. The principal investigator or the designee shall notify the information required for allocation in addition to the study subject identification (ID) code. Then, drugs that should be administered to each study subject will be notified through the Case Registration Web System. The principal investigator or investigator shall prescribe the study drug or comparative drug according to the notification, and record the drug information (the name, dose per administration, number of daily administration and number of tablets per administration) into the CRF of each research subject.

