10.1.10 Actions taken for the study drug or comparative drug

Actions taken for the study drug or comparative drug shall be classified or defined as shown below.

Drug withdrawn	
The study drug or comparative drug is discontinued because of an adverse event (including withdrawal by the study subject at his/her own discretion).
 
When the study is discontinued but administration of the study drug or comparative drug is still continued, the classification should be “Dose not changed.”

Dose not changed	
The dose was not changed after the onset of the adverse event.
 
The study drug or comparative drug was discontinued, reduced, or increased because of another adverse event.
 
The study drug was discontinued or reduced for a reason other than the adverse event, e.g., inadvertence of the study subject.

Unknown	It has not been possible to determine what action has been taken because the study subject is lost to follow-up.
Not Applicable	The administration of the study drug or comparative drug had already been completed or discontinued before the onset of the adverse event.
Dose reduced	The dose of the study drug or comparative drug is reduced because of an adverse event (including dose reduction by the study subject at his/her own discretion).
Dose increased	The dose of the study drug or comparative drug was increased because of the adverse event (including dose increase by the study subject at his/her own discretion).
Washout	If administration of the study drug or comparative drug is suspended (i.e., interrupted) (including suspension/interruption by the study subject at his/her own discretion) because of the adverse event but resumed thereafter, shall be defined as “washout”.

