Planned Number of Dosage of Trelagliptin (tablets)	(The last administration date - the first administration date) / 7) +1. * Cut off to the whole number	All data must not be missing.
Planned Number of Dosage of Daily DPP -4 Inhibitor (tablets)	(The last administration date - the first administration date) \times number of daily dose \times number of tablets at the first administration date	All data must not be missing.
Study Medication Compliance (%)	Actual number of dosage / Planned number of dosage \times 100 (tablets)	All data must not be missing.
Days after Administration (Days)	Examination/observation/evaluation date - the first administration date +1	All data must not be missing.

Items	Method	Conditions
Duration of Diabetes (year)	$\{ (\text{The first administration date (year)} \times 12 + \text{The first administration date (month)}) - (\text{Onset Date of Diabetes (year)} \times 12 + \text{Onset Date of Diabetes (month)}) \} / 12$ (rounded off two decimal places)	All data must not be missing. If only the month of the onset of diabetes is unknown, the month of the onset of diabetes is regarded as "January".
8-OHdG/Creatinine (ng/mg CRE)	8-OHdG (ng/mL) / Urine creatinine (mg/dL) $\times 100$	All data must not be missing.

Display digit

Item	Defitintion
Mean, Confidence interval, Quartiles	Round statistics down to the 1 digits lower than significant digits of the data.
Standard Deviation	Round to the 2 digits lower than significant digits of the data.
Minimum and Maximum Values	Display the data at the significant digits.
Proportion, Percentage	Round to the one decimal place.
P-value	Round down to four decimal places. If p-value is less than 0.0001, display "p<0.0001"

AE related to Hypoglycaemia

AE related to Hypoglycaemia is defined as below.

PT Code	PT Name (Japanese)	PT Name (English)
10020993	低血糖	Hypoglycaemia
10040576	低血糖ショック	Shock hypoglycaemic
10065981	低血糖性意識消失	Hypoglycaemic unconsciousness
10048803	低血糖性痙攣	Hypoglycaemic seizure
10021002	低血糖性脳症	Hypoglycaemic encephalopathy
10021000	低血糖昏睡	Hypoglycaemic coma
10020997	無自覚性低血糖	Hypoglycaemia unawareness
10054998	神経低糖症	Neuroglycopenia

1 SUBJECTS, DEMOGRAPHIC and OTHER BASELINE CHARACTERISTICS

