1.2.4 Dosing conditions of Study drug

Analysis Set: Full Analysis Set

Items: Trelagliptin (mg/week) [50, 100, Other]

Control Drugs [Sitagliptin, Vildagliptin, Alogliptin, Linagliptin, Teneligliptin, Anagliptin, Saxagliptin]

Control Drug(mg/day)

Sitagliptin [25, 50, 100, Other]

Vildagliptin [50, 100, Other]

Alogliptin	[25, Other]
Linagliptin	[5, Other]
Teneligliptin	[20, 40, Other]
Anagliptin	[200, 400, Other]
Saxagliptin	[2.5, 5, Other]

Method: (1) Frequency distribution at Week 0.

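### Planned daily-arm tablets are frozen at the first-day tablet count, so compliance is mis-scored for any daily subject whose prescribed tablet count changes

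*SAP*

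**What the plan says.** The SAP defines compliance in its Other Data Handling table as "Actual number of dosage / Planned number of dosage", times 100, in tablets.

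- **Daily arm.** Planned tablets start from "The last administration date - the first administration date". This is multiplied by the number of daily doses and by the "number of tablets at the first administration date". There is no provision for a later count.
- **Weekly arm.** Planned tablets are "The last administration date - the first administration date) / 7) +1", cut to a whole number. The row is labelled in tablets but has no term for tablets per dose.

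The protocol allows for changes during treatment:

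- Section 9.2.3 has the study or comparative drug prescribed again at Week 4.
- Section 8.1.2 leaves comparator dosing to each package insert.
- Section 10.1.10 has action categories for a reduced and an increased dose of either drug, the latter worded "The dose of the study drug or comparative drug was increased because of the adverse event".
- Section 8.4 has the investigator record in the CRF the "number of daily administration and number of tablets per administration".

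Section 8.3 restricts changes to concomitant medication. I found no section that fixes the study or comparative drug dose for the 12 weeks.

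Protocol 5.2.3 lists compliance among the Other Endpoints. SAP 2.3 summarises it by treatment group without a test.

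**The concern.** The numerator follows what the subject actually took, whereas the denominator stays at the first-day prescription. When the prescribed number of tablets changes, the ratio measures the change in prescription as well as adherence. A subject who does exactly as told then appears to over-use or under-use the drug. A subject who ignores an increase can appear fully compliant.

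The measure matters for interpretation. Protocol 4.1 argues for weekly dosing partly on expected adherence, and the compliance summary is where the report would show that by arm. The frozen tablet count appears only in the daily-arm formula, so the distortion falls on one side of the comparison.

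**Working it through.** The documents state no compliance figure, so there is none to reproduce. The formulas are applied to subjects dosing on Days 1 to 84 (12 weeks, Protocol 6.1). The changes in tablet count are assumptions. Day 29 is used because it follows a Week 4 prescription.

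**SAP rule, daily arm:** planned = (last date − first date) × daily doses × first-day tablets. For Days 1 to 84 the first term is 84 − 1 = 83.

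**No change (reference).** One tablet once daily: 84 taken against 83 planned = 101.2%. The excess comes from the missing +1. The weekly row has that +1, and so does the days-after-administration row ("Examination/observation/evaluation date - the first administration date +1"). This is a separate matter, so results are shown both ways.

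**Prescribed count changes, full adherence:**

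| Prescribed change | Taken | Planned (SAP) | Compliance | With day count of 84 |
|---|---|---|---|---|
| 1 to 2 tablets from Day 29 | 28×1 + 56×2 = 140 | 83×1 = 83 | 168.7% | 140/84 = 166.7% |
| 2 to 1 tablets from Day 29 | 28×2 + 56×1 = 112 | 83×2 = 166 | 67.5% | 112/168 = 66.7% |
| 1 to 2 tablets from Day 57 | 56×1 + 28×2 = 112 | 83×1 = 83 | 134.9% | 112/84 = 133.3% |
| 2 to 1 tablets from Day 57 | 56×2 + 28×1 = 140 | 83×2 = 166 | 84.3% | 140/168 = 83.3% |

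Correcting the day count barely moves these values, so the frozen tablet count is an error of its own.

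**Masking.** A subject prescribed 1 then 2 tablets from Day 29 who keeps taking 1 has 84 taken against 83 planned = 101.2%. Against the prescription it is 84/140 = 60.0%.

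**Strength changes, count does not.** Taken and planned both stay at one tablet a day, giving 84/84 = 100% with the day count corrected. No error arises.

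**Dosing frequency.** The SAP does not say whether the number of daily doses is also read at the first date. If it is, a change from once to twice daily at Day 29 with one tablet per dose gives the same 140/83 = 168.7%, and the reverse gives 112/166 = 67.5%.

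**After the fix.** Planned = 28×1 + 56×2 = 140 or 28×2 + 56×1 = 112. Both adherent subjects score 100%.

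**Weekly arm.** Twelve doses span 77 days, so planned = 77/7 + 1 = 12. With one tablet per dose the ratio is 12/12 = 100%, including when one 100 mg tablet becomes one 50 mg tablet. The formula is right exactly when each dose is one tablet, and the documents do not say whether it is.

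**The case against.** The strongest reply is that nothing shows prescribed tablet counts will change. There is no titration scheme, and the Week 4 prescription may be simple resupply. The several mg/day levels in SAP 1.2.4 are categories for a "Frequency distribution at Week 0", so they describe differences between subjects at the start, not changes within a subject. The 10.1.10 categories apply to actions taken because of an adverse event. They also include changes made at the subject's own discretion, which are non-adherence and are properly scored against the prescription.

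Much of this stands. It means the frequency is unknown and may be zero, and that subject-initiated changes must not be absorbed into the planned count. It does not rescue the rule. The same categories also cover changes that the subject did not initiate, and the SAP then gives a wrong number.

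A reader might go further in four ways that the documents do not support:

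- **Any dose change is mis-scored.** Only a change in tablet count matters.
- **The weekly formula is wrong.** It is exact at one tablet per dose, and no tablet strength or count is given to show otherwise.
- **The daily-arm mean is biased by a stated amount.** No share of subjects with changes is given, so none can be calculated.
- **The comparator arm's treatment over 12 weeks cannot be reconstructed.** The SAP section 4 listings give, by subject, dose dates and times, quantities dispensed and unused, and action taken for adverse events. SAP 1.2.4 is a baseline table, so its restriction to Week 0 is not a defect.

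**Conclusion.** The concern holds for daily-arm subjects whose prescribed tablet count changes during treatment. Full adherence then scores between 67.5% and 168.7% in the cases shown. With the day count corrected, the Day 29 changes still give 66.7% and 166.7%. These figures rest on assumed changes of one tablet a day at Day 29 or Day 57. The group-level effect cannot be sized.

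The consequence is limited. Compliance is an untested, descriptive measure that defines no analysis set and enters no ANCOVA, so the primary and secondary results do not depend on it. The rule is still worth repairing, because it is stated explicitly, gives a wrong value when followed, and is cheap to correct. In the weekly arm the documents support only a request to state the tablets-per-dose assumption.

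**What to change.** In SAP Other Data Handling:

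1. **Daily arm.** Define planned tablets as the sum over prescription periods of scheduled administrations in the period (first and last dosing day included) times the tablets per administration prescribed in that period. Alternatively, define compliance by administrations taken over administrations scheduled, which removes the tablet count altogether. Either way, use the dosing frequency in force in each period.
2. **Subject-initiated changes.** State that planned tablets follow the investigator's prescription, so that a change made by the subject counts as a departure from plan.
3. **Trelagliptin row.** Add the tablets-per-administration factor, or state that each weekly dose is one tablet.

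The cost is SAP wording and programming, with no new visits or subjects. One point needs checking first. Protocol 8.4 has tablets per administration recorded when the drug is prescribed after allocation, but no section expressly requires it to be recorded again at Week 4. If the CRF does not capture it there, the quantities prescribed and unused (Protocol 9.1.11) and the dispensing listing (SAP section 4) are the places to look for it.

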1.1 Subject Disposition

1.1.1 Study Information

Analysis Set: All subjects who are obtained informed consent

Items: Date of First Subject Signed Informed Consent Form
Date of Last Subject's Last Dose/Last Observation/Last Examination
MedDRA Version
SAS Version

Method : For the above analysis items, the following analysis will be performed.
(1) Display the above items

1.1.2 Eligibility of Subjects

Analysis Set: All subjects who are obtained informed consent

Items: Randomization into the Treatment [Yes, No]
Period of the Study
Reason for Not randomized [Major Protocol Deviation, Lost to Follow-Up, Voluntary Withdrawal, Study Termination, Pregnancy, Did not meet entrance criteria, Other]

Method : For the above analysis items, the following analysis will be performed.
The denominator for the reasons is the number of subjects of Not randomized.
(1) Frequency distribution

1.1.3 Disposition of Subjects

Analysis Set: All Randomized subjects

Items: Status at the End of Study [Completed, Not Completed]
Reason for Not Completed [Adverse Event, Major Protocol Deviation, Lost to Follow-Up, Voluntary Withdrawal, Study Termination, Pregnancy, Lack of Efficacy, Other]

Method : For the above analysis items, the following analysis will be performed for each treatment group and total.
The denominator for the reasons is the number of subjects of Not completed.

(1) Frequency distribution

1.1.4 Protocol Deviations

Analysis Set: All Randomized subjects

Items: Protocol Deviations [Major GCP Violation, Deviations of Protocol Entry Criteria, Deviations Related to Treatment Procedure or Dose, Deviations Concerning Excluded Medication or Therapy, Deviation to Avoid Emergency Risk, Other]

Method: For the above analysis items, the following analysis will be performed for each treatment group and total. Summarize the number of subjects who have deviated from the protocol, classify the deviations into the above category, and show the breakdown of deviations. Subjects applicable for multiple categories will be counted once in each category.

(1) Frequency distribution

1.1.5 Datasets Analyzed

Analysis Set: All Randomized subjects

Items: Subjects Included/Excluded from Analysis Sets

Full Analysis Set [Inclusion]

Safety Analysis Set [Inclusion]

Method: For the above analysis items, the following analysis will be performed.

(1) Frequency distribution

1.2 Demographics and Other Baseline Characteristics**1.2.1 Distribution of Demographics Items**

Analysis Set: Full Analysis Set

Items: Age (years) [Min<= - <65, 65<= - <75, 75<= - <=Max]

Gender [Male, Female]

Height (cm) [Min<= - <150, 150<= - <160, 160<= - <170, 170<= - <=Max]

Weight (kg) [Min<= - <50.0, 50.0<= - <60.0, 60.0<= - <70.0, 70.0<= - <80.0, 80.0<= - <=Max]

BMI (kg/m2) [Min<= - <18.5, 18.5<= - <25.0,

	25.0<= - <=Max]
Smoking Classification	[Never smoked, Current smoker, Ex-smoker]
Drink Alcohol Almost Every Day?	[Yes, No]
Duration of type 2 Diabetes Mellitus (years)	[Min<= - < 5, 5<= - <10, 10<= - <=Max]
Any Medication for Concurrent Condition?(Week 0)	[Yes, No]
Number of Daily Doses of Drugs (Concurrent Condition Medicine.)	[Less than 2 Times, 2 Times or More]
Total Number of Daily Tablets (Concurrent Condition Medicine.)	[Less than 2 Tablets, 2 Tablets or More]
Number of Doses of Drugs (Study drug.)	[Once a Week, Once daily, Twice daily]
HbA1c (Week -4)	[Less than 8.0%, 8.0% or more]
DTR -QOL Total Score (Week -4)	[Less than 80, 80 or more]
DTR -QOL Total Score (Week 0)	
DTR -QOL Total Score of "Factor 1: Burden on Social Activities and Daily Activities" (Week 0)	
DTR -QOL Total Score of "Factor 2: Anxiety and Dissatisfaction with Treatment" (Week 0)	
DTR -QOL Total Score of "Factor 3: Hypoglycemia" (Week 0)	
DTR -QOL Total Score of "Factor 4: Satisfaction with Treatment" (Week 0)	
DTSQ Total Score (Week 0)	
Method:	For the above analysis items, the following analysis will be performed for each treatment group and total.
	(1) Summary of frequency distribution for discrete variables and summary statistics for continuous variables.

1.2.2 Medical History and Concurrent Disease

Analysis Set: Full Analysis Set

Items: Medical History

Concurrent Medical Conditions

Method: For the above analysis items, the following analysis will be performed for each treatment group and total.

Analysis variables will be coded using the MedDRA dictionary and be summarized into SOC and PT. SOCs will be sorted in alphabetical order, then PTs will be sorted in frequency order.

(1) Medical history: Summary of frequency distribution by SOC/PT

(2) Concurrent medical conditions: Summary of frequency distribution by SOC/PT

The method of accounting for the frequency is as follows.

[Number of subjects]

For each summary, subjects with one or more events within a level of SOC term is counted only once in that level. Similarly, subjects with one or more events within a level of PT term is counted only once in that level.

1.2.3 Concomitant Medications

Analysis Set: Full Analysis Set

Items: Concomitant Medication

Method: For the above analysis items, the following analysis will be performed for each treatment group and total. Analysis variables will be coded using the WHO (World Health Organization) Drug. Coded medications will be sorted in frequency order. Medications used more than once within a subject will be counted only once for the subject.

(1) Frequency distribution

1.2.4 Dosing conditions of Study drug

Analysis Set: Full Analysis Set

Items: Trelagliptin (mg/week) [50, 100, Other]

Control Drugs [Sitagliptin, Vildagliptin, Alogliptin, Linagliptin, Teneligliptin, Anagliptin, Saxagliptin]

Control Drug(mg/day)

Sitagliptin [25, 50, 100, Other]

Vildagliptin [50, 100, Other]

Alogliptin	[25, Other]
Linagliptin	[5, Other]
Teneligliptin	[20, 40, Other]
Anagliptin	[200, 400, Other]
Saxagliptin	[2.5, 5, Other]

Method: (1) Frequency distribution at Week 0.

2 EFFICACY EVALUATIONS

2.1 Primary Endpoint and the Analytical Methods

Analysis Set: Full Analysis Set

Items: Change from Baseline in DTR-QOL Total Score at End of Study (Week 12)

Method: Analysis of covariance (ANCOVA) is conducted to compare between the treatment groups using "Change from baseline in DTR-QOL total score by the end of treatment [the End of Study (Week 12) - baseline (Week 0)]" as a dependent variable; DTR-QOL Total Score at the start of the screening period(<80 or ≥ 80) and HbA1c ($<8.0\%$ or $\geq 8.0\%$) at the start of the screening period as covariates; and "treatment group" as an independent variable. The level of significance is defined as 5% (two-sided).

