- Change from baseline (Week 0) in total score for all question items in the DTR-QOL Questionnaire at the end of the treatment period (Week 12).
 - (1) A comparison between the treatment groups will be carried out based on the ANCOVA model using a change in the total score by the end of treatment [the end of the treatment period (Week 12) - baseline (Week 0)] as a dependent variable; the total score at the baseline (Week 0), the total score of the DTR-QOL Questionnaire (<80% or ≥80%) at the start of the screening period and HbA1c (<8.0% or ≥8.0%) at the start of the screening period as covariates; and a treatment group as an independent variable. The level of significance will be 5% (two-sided).

<Secondary endpoints>

Efficacy endpoints:

- Change in the total score for each factor provided through the DTR-QOL Questionnaire [“Factor 1: Burden on social activities and daily activities (13 questions in all)”, “Factor 2: Anxiety and dissatisfaction with treatment (8 questions in all)”, “Factor 3: Hypoglycemia (4 questions in all)”, and “Factor 4: Treatment satisfaction (4 questions in all)”] at each assessment time point.
- Change in the total score for all questions in the DTR-QOL Questionnaire at each assessment time point.
- Change in the total score for treatment satisfaction in the DTSQ at each assessment time point.
 - (1) Summary statistics [sample size, mean, standard deviation (SD), maximum, minimum and quantile] and the two-sided 95% confidence interval (CI) for means per treatment group at each assessment time point will be calculated to plot the changes in means and SDs. Point estimates and the two-sided 95% CI for differences between the treatment groups will also be calculated.
 - (2) Changes from the baseline (Week 0) to each assessment time point will be calculated to be similarly analyzed to 1) above.

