Treatment compliance of each study subject will be calculated and summary statistics of compliance per treatment group will be presented.
- The Basic Information on Study Subject (Your Basic Profile)
Frequency of answers to each question at each visit will be analyzed per treatment group.

CONFIDENTIAL

Rationale for the number of planned study subjects:

In this clinical study, to discuss the changes in the total score for all questions in the DTR-QOL Questionnaire from the baseline (Week 0) to the end of the treatment period, as the primary endpoint, mean changes in the daily DPP-4 inhibitor and trelagliptin groups were assumed as 14.4% and 19.0%, respectively. The mean change in the daily DPP-4 inhibitor group was assumed by reference to the data on a sodium glucose transporter 2 (SGLT2) inhibitor, from the previous research; and that in trelagliptin group was assumed by reference to the data from the validation trial of the DTR-QOL Questionnaire. The common SD was assumed as 12.1 % considering the former assumption. When 5% of significance level (two-sided) is based for the analysis of the primary endpoint, 110 subjects per group would be needed to ensure 80% power in comparisons between the trelagliptin group and daily DPP-4 inhibitor group. As this is a study on treatment for type 2 diabetes with DPP-4 inhibitors currently used in the medical setting, the number of randomized subjects was established as 120 subjects per group, for a total of 240 subjects, assuming a type 2 diabetes treatment discontinuation rate of 8%*.

*Based on the results for Topic 2 of the “Strategic Studies on the Prevention of Diabetes” (JDOIT-2), the annual discontinuation rate for the “usual care group” without intervention is approximately 8%.

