13.1.3 Efficacy analysis

From FAS the following shall be analyzed.

<Primary endpoint>

Change from baseline (Week 0) in total score for all question items in the DTR-QOL Questionnaire at the end of the treatment period (Week 12).

- 1) A comparison between the treatment groups will be carried out based on the ANCOVA model using "the change in the total score by the end of treatment [the end of the treatment period - baseline (Week 0)]" as a dependent variable; "the total score at the baseline, the total score of the DTR-QOL Questionnaire (<80% or ≥80%) at the start of the screening period and HbA1c (<8.0% or ≥8.0%) at the start of the screening period as covariates; and "a treatment group" as an independent variable. The level of significance will be 5% (two-sided).

<Secondary endpoints>

Efficacy endpoints:

- Changes in the total score for each factor provided through the DTR-QOL Questionnaire [“Factor 1: Burden on social activities and daily activities (13 questions in all)”, Factor 2: Anxiety and dissatisfaction with treatment (8 questions in all), “Factor 3; Hypoglycemia (4 questions in all)”, and “Factor 4: Treatment satisfaction (4 questions in all)”] at each assessment time point.
- Change in the total score for all questions in the DTR-QOL Questionnaire at each assessment time point.
- Change in the total score for treatment satisfaction in the DTSQ (evaluated with the score of questions #1, 4, 5, 6, 7, and 8) at each assessment time point.
 - 1) Summary statistics [sample size, mean, standard deviation (SD), maximum, minimum and quantile] and the two-sided 95% confidence interval (CI) for means per treatment group at each assessment time point will be calculated to plot the changes in means and SDs. Point estimates and the two-sided 95% CI for differences between the treatment groups will also be calculated.
 - 2) Changes from the baseline (Week 0) to each assessment time point will be calculated to be similarly analyzed to 1) above.

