 - 3) The analyses below carried out on the total score for each factor provided through the DTR-QOL Questionnaire, and on the total score for treatment satisfaction in the DTSQ: A comparison between the treatment groups will be carried out based on the ANCOVA model using "the change in the total score by the end of treatment [the end of the treatment period (Week 12) - baseline (Week 0)]" as a dependent variable; the total score at the baseline (Week 0), the total score of "the DTR-QOL Questionnaire (<80% or \geq 80%)" at the baseline (Week 0) and "HbA1c (<8.0% or \geq 8.0%)" at the baseline (Week 0) as covariates; and "a treatment group" as an independent variable. The level of significance will be 5% (two-sided). Note that the total score for all questions in the DTR-QOL is out of the scope of the analysis.
 - 4) To indicate the changes in the total scores for all questions in the DTR-QOL Questionnaire and the total scores for treatment satisfaction in the DTSQ, the summary statistics and two-sided 95% CI for means per treatment group will be calculated, with stratification by the following factors at the start of the treatment period (Week 0):
 - Use of medication for treatment of comorbidities
 - Number of daily doses of medication for treatment of comorbidities (<2 times or \geq 2 times)

- Total number of daily tablets of medication for treatment of comorbidities (<2 tablets or ≥ 2 tablets)
- Number of doses of the study drug or comparative drug (once weekly, once daily or twice daily)
- Changes in the scores per question in the DTR-QOL Questionnaire at each assessment time point.
- Changes in the scores for per question in the DTSQ at each assessment time point.
 - 1) Summary statistics for measurements and the changes from the baseline (Week 0) will be calculated per treatment group.

<Other endpoints>

Summarizations below will be performed in the "full analysis set" (FAS).

- Laboratory tests
Treatment compliance of each study subject will be calculated and summary statistics of compliance per treatment group will be presented.
- Treatment compliance
Treatment compliance of each study subject will be calculated and summary statistics of compliance per treatment group will be presented.
- The Basic Information on Study Subject (Your Basic Profile)
Frequency of answers to each question at each visit will be analyzed per treatment group.

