2.2 Secondary Endpoints and the Analytical Methods

Analysis Set: Full Analysis Set

Items: 1) DTR -QOL Total Score
2) DTR -QOL Total Score of Factor1 to Factor 4
"Factor 1: Burden on Social Activities and Daily Activities" (13 questions)
"Factor 2: Anxiety and Dissatisfaction with Treatment" (8 questions)
"Factor 3: Hypoglycemia" (4 questions)
"Factor 4: Satisfaction with Treatment" (4 questions)
3) DTSQ Total Score
4) DTR -QOL Total Score of Each Items
5) DTSQ Total Score of Each Items

Analysis Visit: Week 0, Week 4, Week 12, End of Study

Method:

- (1) The following analysis will be performed for the Items 1 to 3 described above.
 Summary statistics of observed value and 95% confidence interval for the mean will be calculated by treatment groups and Analysis Visit. In addition, Mean (+/-SD) plots will be made by treatment group and Analysis Visit. Adjusted mean differences and the 95% confidence interval (two-sided) will also be provided. The same analyses described above will be performed on change from baseline at each analysis visit.
- (2) The following analysis will be performed for the Items 2 to 3 described above.
 Analysis of covariance (ANCOVA) will be conducted to compare between the treatment groups using "the change from baseline in the total score by the end of treatment [the End of Study(Week 12) - baseline (Week 0)]" as a dependent variable; the total score of "the DTR-QOL Total score (<80 or ≥ 80)" at the baseline (Week 0) and "HbA1c (<8.0% or $\geq 8.0\%$)" at the baseline (Week 0) as covariates; and "a treatment group" as an independent variable.
- (3) The following analysis will be performed for the Items 1, 3 described above.
 The summary statistics and two-sided 95% CI for means of change from baseline by treatment group will be calculated, with stratification by the following factors at the start of the treatment period (Week 0):
 - Use of medication for treatment of comorbidities;
 - Number of daily doses of medication for treatment of comorbidities (<2 times or ≥ 2 times);
 - total number of daily tablets of medication for treatment of comorbidities (<2 tablets or ≥ 2 tablets);
 - Number of doses of the study drug or comparative drug (once weekly, once daily or twice daily).
- (4) The following analysis will be performed for the Items 4 -5 described above.
 Summary statistics for measurements and the change from baseline (Week 0) will be calculated by treatment group per question at each analysis visit.

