2.4 CONSIDERATIONS on STATISTICAL ANALYSIS

2.4.1 Adjustments for Covariates

ANCOVA will be performed on primary and secondary endpoints using treatment group as independent variables. Details are described in 2.1 and 2.2

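### The SAP's primary ANCOVA omits the Week 0 DTR-QOL score that the protocol lists as a covariate, and its secondary ANCOVAs omit each endpoint's own Week 0 score

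*SAP*

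**What the plan says.** **Primary endpoint.** Protocol 13.1.3 lists, before the HbA1c stratum, "the total score at the baseline, the total score of the DTR-QOL Questionnaire" dichotomised at 80% at screening. The synopsis (2.0) has the same list with the visit named: "the total score at the baseline (Week 0), the total score of the DTR-QOL Questionnaire". That makes three covariates: Week 0 score, screening DTR-QOL stratum, screening HbA1c stratum. The protocol does not use the word continuous for the Week 0 score, but it lists the score without cut-points next to two variables that have them.

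SAP 2.1 goes straight from the outcome to the strata: "as a dependent variable; DTR-QOL Total Score at the start of the screening period", cut at 80, then HbA1c cut at 8.0%. There are two covariates.

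**Factor scores and DTSQ.** Protocol 13.1.3, secondary item 3, begins its list with "the total score at the baseline (Week 0), the total score of" and continues with the DTR-QOL and HbA1c categories at Week 0. SAP 2.2 method (2) reads "as a dependent variable; the total score of" the DTR-QOL category, then the HbA1c category. The endpoint's own Week 0 score is missing.

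**Elsewhere in the SAP.** Section 2.4.1 says "ANCOVA will be performed on primary and secondary endpoints using treatment group as independent variables" and sends the reader back to 2.1 and 2.2. The revision history attributes version 2.0 to the revised protocol, but both protocol versions in the file carry the Week 0 covariate.

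**The concern.** The outcome is Week 12 minus Week 0 on a bounded 0–100 scale. Such a change is expected to be negatively related to its starting value, through regression to the mean and the ceiling. Leaving Week 0 out of the model leaves that variation in the error term and lets a chance Week 0 difference between arms pass into the treatment estimate. A two-level flag from an earlier visit recovers only part of it. The DTSQ is worse placed: it is not administered at screening, so its model contains no baseline value of that instrument.

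There is also a problem that needs no assumption about correlations. The protocol and the SAP specify different primary tests for an open-label trial. An analyst following the SAP will not run the protocol's analysis, and if the two disagree, nothing says which one decides.

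**Working it through.** **1. Reproduce the plan's sample size.** Inputs are from protocol 13.3 and the synopsis: "mean changes in the daily DPP-4 inhibitor and trelagliptin groups were assumed as 14.4% and 19.0%, respectively", so the difference is 19.0 − 14.4 = 4.6; common SD 12.1; two-sided 5%; 80% power.

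- Normal approximation: n = 2 × [12.1 × (1.960 + 0.842) / 4.6]² = 108.6, so 109 per group.
- Two-sample t-test (noncentral t): 110 per group, power 0.801.
- Discontinuation: 110 / 0.92 = 119.6, so 120 per group.

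The stated 110 and 120 are reproduced by an unadjusted comparison of change scores. I therefore read 12.1 as the SD of change.

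**2. Assumptions the documents do not supply.**

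- ρ, the Week 0 to Week 12 correlation: 0.3–0.7, with 0.8 as an extra case.
- r, the screening to Week 0 correlation: 0.7–0.9.
- Screening cut-point c: 0 to 0.8 SD above the mean.
- Normal scores with equal variances. Screening is related to Week 12 only through Week 0 (structure A). The HbA1c stratum is left out of both models.

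**3. Residual variance as a fraction of 12.1².** Let p be the share above the cut, φ the normal density, and k = φ(c)² / [p(1 − p)]. Then k = 0.637 at c = 0 and 0.503 at c = 0.8.

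- SAP model: 1 − r²k(1 − ρ)/2
- Protocol model: (1 + ρ)/2

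For ρ = 0.5 and r = 0.8:

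- SAP: 1 − 0.64 × 0.637 × 0.25 = 0.898, SD 12.1 × √0.898 = 11.5. With k = 0.503: 0.920, SD 11.6.
- Protocol: 0.75, SD 10.5.
- Variance reduction: 1 − 0.75/0.898 = 16%, to 1 − 0.75/0.920 = 18%.
- Power at 110 per group: 83–84% (SAP), 90% (protocol).

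**4. Shift from chance Week 0 imbalance under the SAP model, at the 95% limit.** The score SD is 12.1/√[2(1 − ρ)], and

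shift = 1.96 × score SD × √(1 − r²k) × √(2/110) × (1 − ρ).

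For ρ = 0.5, r = 0.8, k = 0.637: 1.96 × 12.1 × 0.770 × 0.135 × 0.5 = 1.2 points. With k = 0.503 it is 1.3.

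**5. Over the assumed ranges of r and c (structure A).**

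| ρ | Residual SD, SAP | Residual SD, protocol | Variance reduction | Power, SAP | Power, protocol | 95% shift, points |
|---|---|---|---|---|---|---|
| 0.3 | 11.0–11.6 | 9.8 | 21–29% | 84–87% | 94% | 1.3–1.6 |
| 0.5 | 11.3–11.7 | 10.5 | 14–20% | 83–85% | 90% | 1.1–1.4 |
| 0.7 | 11.6–11.9 | 11.2 | 8–12% | 82–83% | 86% | 0.9–1.1 |
| 0.8 | 11.8–12.0 | 11.5 | 5–8% | 81–82% | 84% | 0.7–0.9 |

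For ρ from 0.3 to 0.7 the gain is about 3–10 power points. The shift of 0.9–1.6 points is about 19–36% of 4.6.

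**6. Sensitivity to the unknown screening to Week 12 correlation.** If screening correlates with Week 12 as strongly as Week 0 does (structure B), the reduction reaches about 31% and the gain about 11 points. At ρ = 0.5 and r = 0.8, SAP-model SD is about 11.8 and power about 82%, against 10.4 and 90% for the protocol model.

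**The case against.** The omission is not disputed; the dispute is over how much it harms.

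- **Planned power is met.** The 110 per group came from an unadjusted test, so no gain from a baseline covariate was relied on. With 12.1 as the SD of change, SAP-model power is at least 80% throughout. This stands: what is lost is precision beyond the plan. Only if 12.1 were already a baseline-adjusted SD would power fall short, to about 66–78% (ρ 0.3–0.8, r 0.7–0.85), and step 1 does not suggest that reading.
- **The test remains valid.** Under randomisation the SAP model is unbiased and keeps its type I error. The imbalance shift is already reflected in its wider confidence interval, so imbalance and lost precision are largely one loss seen two ways. This stands, and the two should not be added together.
- **Some baseline information remains.** The primary model keeps the screening stratum, on which randomisation was also stratified. The secondary models keep a dichotomised Week 0 DTR-QOL total. The loss is therefore partial, as the working allows. For the DTSQ, no baseline value of that instrument is left.
- **The size depends on assumed correlations.** This stands. At ρ = 0.8 under structure A the gain is only 2–3 points.
- **The protocol leaves detailed methods to the SAP (13.1).** Giving detail is not the same as dropping a covariate the protocol names, and no reason is recorded.

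These points limit the harm. None of them reconciles the two primary models.

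**Conclusion.** The concern holds. The mismatch is plain from the text, appears separately in SAP 2.1 and 2.2, and is not explained by a protocol revision. Run as written, the SAP delivers a different and less precise primary test than the protocol specifies.

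The conflict between the documents rests on no assumption and is reason enough to require correction. The precision loss depends on correlations the documents do not give: about 8–31% of residual variance and 3–11 power points over ρ 0.3–0.7 and r 0.7–0.9, taking both correlation structures together. Neither the planned 80% power (with 12.1 as the SD of change) nor the type I error is compromised.

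**What to change.** - In SAP 2.1, add the DTR-QOL total score at Week 0, as a continuous covariate, to the two screening strata.
- In SAP 2.2 method (2), add the continuous Week 0 value of the score being analysed: the relevant factor score, or the DTSQ total.

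If the omission was deliberate, the alternative is to record the reason before database lock, bring the protocol and SAP into agreement, and state which model is primary.

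The cost is one line in each section. Both questionnaires are completed at Week 0 (protocol 9.2.2) and the Week 0 scores are already tabulated (SAP 1.2.1). Adding the covariates needs no new data and no protocol amendment.
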